## **Statement of Compliance**

This study will be conducted in accordance with the Code of Federal Regulations on the Protection of Human Subjects (45 CFR Part 46), any other applicable US government research regulations, and institutional research policies and procedures. The Principal Investigator will assure that no deviation from, or changes to the protocol will take place without prior agreement from the sponsor and documented approval from the Institutional Review Board (IRB), except where necessary to eliminate an immediate hazard(s) to the trial participants. All personnel involved in the conduct of this study have completed Human Subjects Protection Training.

CONFIDENTIAL

## List of Abbreviations

AE	Adverse Event/Adverse Experience
AES	Adult Emergency Services (Bellevue Hospital)
DSMB	Data and Safety Monitoring Board
ED	Emergency Department
FFR	Federal Financial Report
FWA	Federalwide Assurance
GCP	Good Clinical Practice
HIPAA	Health Insurance Portability and Accountability Act
HRST	Homelessness Risk Screening Tool
ICF	Informed Consent Form
IRB	Institutional Review Board
N	Number (typically refers to participants)
NIH	National Institutes of Health
OHRP	Office for Human Research Protections
OHSR	Office of Human Subjects Research
PES	Pediatric Emergency Services (Bellevue Hospital)
PI	Principal Investigator
RA	Research Assistant
RC	Research Coordinator
QA	Quality Assurance
QC	Quality Control
SAE	Serious Adverse Event/Serious Adverse Experience
SOP	Standard Operating Procedure
UC	Urgent Care (Bellevue Hospital)

Throughout this document, attachments (e.g., study surveys and other instruments) are designated using *underlined italic* font.

### CONFIDENTIAL

## Protocol Summary

[figure not shown]
Title	ED-Home: A pilot feasibility study of a homelessness prevention intervention for substance using emergency department patients
Short Title	ED-Home
Brief Summary	This is a single-arm pilot study to test the feasibility of homelessness prevention and substance use interventions to be delivered to at-risk patients in the Bellevue Hospital emergency department (ED). ED patients (n=40) found eligible for the study will complete a baseline survey and receive referrals to appropriate services, with a final six-month follow-up survey. Interim contacts at 7-10 days, 3 months, and 5 months will be used to assure intervention components were received and to confirm participant contact information. A chart review of participant Bellevue Hospital Center visits will also be performed at the time of the six-month follow-up visit.
Phase	N/A
Objectives	The primary objective is to test the feasibility and acceptability of implementing a homelessness prevention intervention for ED patients with unhealthy alcohol or drug use who are at risk for homelessness.
Methodology	Single-arm pilot feasibility study with pre-post outcome measurement.
Endpoint	Primary endpoints are feasibility of the study and intervention (e.g., participant satisfaction, ability to enroll participants, ability to contact participants at follow-up time points). Exploratory outcomes include 6-month housing and substance use measures.
Study Duration	Approximately 1.5 years.
Participant Duration	Participants will complete a final follow-up survey 6 months after enrollment/baseline visit.
Duration of behavioral intervention	The intervention delivered by investigators will consist of one-time, in-person referrals (at the time of the baseline/enrollment ED visit) and up to 3 follow-up trouble shooting phone calls to occur within 3 months of the initial visit.
Population	Adult ( $\geq 18$ years old), ED patients with unhealthy alcohol or drug use who are not currently homeless but who are predicted to have a high risk of future homelessness. Patients must speak English, reside in NYC, not be critically ill, and not currently be incarcerated. Patients will not be excluded based on race or gender. Projected sample size: approximately n=40.
Study Sites	NYULH and Bellevue Hospital Center Emergency Department
Number of participants	Approximately 40 participants are expected to be enrolled.
Description of Study Intervention/Procedure	The intervention will consist of: 1) Referral to Homebase homelessness prevention services offered by community-based organizations in NYC; 2) Referral to substance use services (SBIRT and Addiction Leads) available at Bellevue Hospital; 3) Follow-up to ensure participants receive needed services.
Reference Therapy	Standard ED care, which includes referral to the ED social worker and existing substance use treatment services at provider discretion.
Key Procedures	No invasive procedures will be conducted.
Statistical Analysis	Primary feasibility endpoints will be analyzed using descriptive statistics (proportions, means, etc.). Secondary/exploratory end-points will use appropriate comparisons of baseline and 6-month follow-up data.

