#### **5.5 Duration of Study Participation**

The duration of active study participation is approximately 6 months, with the final follow-up survey with patients occurring 6 months after baseline/enrollment. In cases in which it is difficult to contact or find participants for the follow-up survey, the follow-up visit may be conducted up to 2 months after the 6 month follow-up time period (i.e., up to 8 months after study enrollment). See the [ED-Home Pilot Follow-Up Procedures flow chart](#) in the Study Schema section for details.

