- Homebase information sheet (baseline only): contains name, location, hours, and contact information for the appropriate Homebase office as well as information about Homebase. This referral information will be given to the participants (*ED-Home Homebase Information Sheet*).
- SBIRT (Screening, Brief Intervention, and Referral to Treatment) and/or Addiction Leads services for substance use in ED (as detailed in Section 6)
- Locator form (baseline only): collects detailed contact information from participants to allow for future follow-up (*ED-Home Locator Form*).
- Study contact card and sticker (baseline only): serves as a reminder for the participant's 6 month follow-up visit and contains study staff information to allow participants to contact study staff proactively as needed (*ED-Home Study Contact Card and Sticker*).
- Follow-up phone calls to confirm participant contact information, confirm follow-up appointment, and reschedule missed visits (see ED-Home Follow-Up Procedures Flow Chart in Schematic of Study Design section), documented in REDCap (*ED-Home Tracking Form* and *ED-Home Follow-up Procedures Form*) and tracked using an Excel tracking log for internal study management purposes.
- Follow-up phone calls and/or NYULH SendSafe emails with participants and service providers (e.g., Homebase) to confirm referrals successful and troubleshoot as needed (see ED-Home Follow-Up Procedures Flow Chart in Schematic of Study Design section), documented in REDCap (*ED-Home Tracking Form* and *ED-Home Follow-up Procedures Form*) and tracked using an Excel tracking log for internal study management purposes.
- Mailing a follow-up visit reminder letter containing details of the participant's appointment, documented in REDCap (*ED-Home Follow-up Visit Reminder Letter* and *ED-Home Follow-up Procedures Form*).
- Electronic medical record review for Bellevue Hospital to ascertain information on ED visits, inpatient hospitalizations, outpatient visits, and substance use service visits at Bellevue Hospital (*ED-Home EMR Data Abstraction Tool*).

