***Final Study Visit (6 months, window -2 weeks to +8 weeks)***

- Complete 6 month follow-up survey (see instruments as listed in Section 7.1.1).
- Participant is reminded that this is the final study visit. Participant is thanked for his/her time and has the opportunity to ask any questions about the study.
- Participant given \$50 (cash or gift-card) follow-up reimbursement.

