## 8 Assessment of Safety

### 8.1 Specification of Safety Parameters

This is an extremely low-risk study given the nature of the intervention (referrals to established social services). As such, study endpoints do not include safety parameters. Since the study includes participants with social and medical risks including housing instability and homelessness, we expect that some participants will worsen in status during the course of the study unrelated to the study. Though we will document and respond to any adverse events that we become aware of during the study as described below, we are not performing explicit investigations to attempt to discover adverse events since such events are not expected related to the study. For example, we are not tracking diagnostic test results. We are not tracking hospital stays in real-time. Information about hospitalizations will be recorded retrospectively as an exploratory study outcome as previously described, but such stays will not be considered adverse events.

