### **10.3 Analysis Datasets**

A single analysis dataset will include all participants. The analysis dataset will consist of the following:

- Baseline and follow-up participant surveys and other study instruments.
- Participant locator form information.
- Information collected from follow-up/tracking phone calls and/or NYULH SendSafe emails with participants and/or applicable service providers, as previously described.
- Participant information extracted from approved external sources (with participant consent) including the Bellevue Hospital Center EMR and the NYC DHS CARES dataset.

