#### **10.4.11 Exploratory Analyses**

Planned exploratory analyses will include examining new onset homelessness as measured by entry into a homeless shelter within 6 months of the ED intervention (determined using the Department of Social Services CARES database), multiple self-reported housing status and substance use measures at the 6-month follow-up interview compared to baseline, and measures of health services use. Although we are not powering the study to show statistically significant effects on these outcomes, we will be able to determine feasibility of outcome measurement and gain a preliminary sense of potential intervention effects which may help in determining sample size and other design considerations for future larger studies. Additional exploratory analyses may be conducted based on stakeholder interests and feedback, including as determined during yearly stakeholder meetings.

CONFIDENTIAL

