### CONFIDENTIAL

## Attachment A Schedule of Events

Activity	Baseline [Day 0]	Intermediate Contact 1 [Day 7-10]	Intermediate Contact 1.2 [7-10 days after Intermediate Contact 1, if needed]	Intermediate Contact 1.3 [7-10 days after Intermediate Contact 1.2, if needed]	Intermediate Contact 2 [3 months after Baseline]	Intermediate Contact 3 [5 months after Baseline]	Final Study Visit and Exploratory Outcomes [6 months after Baseline, window -2 to +8 weeks]
Screening							
Screening questions	X						
Eligibility questions	X						
Verify inclusion/exclusion criteria	X						
Verify patient not already in study	X						
Informed consent process	X						
Survey							
ED-Home Survey (REDCap)	X						X
Housing Risk Flyer							X
NYC HRA YouTube video							X
Additional baseline and follow-up questionnaires	X						X
Participant information form	X						
Locator form	X						
Intervention							
Referral to and delivery of Bellevue substance use services	X						
Referral to Homebase services	X						
Troubleshoot unsuccessful Homebase referrals		X	X	X			
Follow-up Phone Calls							
Confirm participant contact information		X			X	X	
Confirm 6-month follow-up visit date		X			X	X	
Document successful Homebase referrals		X	X	X			
Additional Procedures							
Housing resource sheet (ineligible patients only)	X						
Homebase information sheet	X						
Schedule follow-up appointment	X						
Give study contact card and sticker	X						
Reimbursement	X						X
Send 6-month follow-up visit reminder letter						X	
Electronic Medical Record Review							X

CONFIDENTIAL

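### Does tying the chart review to a final visit with a 10-week window leave health-service use without a usable counting period?

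*Combined protocol and SAP*

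**What the plan says.** The Protocol Summary sets the timing: "A chart review of participant Bellevue Hospital Center visits will also be performed at the time of the six-month follow-up visit". Section 7.3.4 heads that visit "Final Study Visit (6 months, window -2 weeks to +8 weeks", and Section 5.5 adds that, for people who are hard to find, "the follow-up visit may be conducted up to 2 months after the 6 month follow-up time period". Attachment A marks the electronic medical record (EMR) review in the column "Final Study Visit and Exploratory Outcomes [6 months after Baseline, window -2 to +8 weeks".

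On content, Section 7.1.1 says the review is "to ascertain information on ED visits, inpatient hospitalizations, outpatient visits, and substance use service visits at Bellevue Hospital", with no date range. Section 8.1 adds: "Information about hospitalizations will be recorded retrospectively as an exploratory study outcome". Sections 4.2.3 and 10.4.11 name health-service use as an exploratory outcome without a period, and Section 4.2.3 points to the EMR Data Abstraction Tool for it. The other record-based outcome does have a period: "entry into a homeless shelter within 6 months of the ED intervention". Section 10.3 says: "A single analysis dataset will include all participants".

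**The concern.** A count of visits means little without the time over which it was taken. Here the review hangs on a visit whose date can move by 10 weeks, and the protocol body gives no start or end date for the count. Two problems seem to follow.

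- A chart opened before month 6 cannot hold six months of visits.
- If visits are counted up to the day the chart is opened, observation time differs between participants. Section 5.5 gives the longest time to those who were hard to contact, and Section 10.4.2 proposes to relate ability to contact to participant characteristics. A link between contactability and service use could then partly reflect unequal observation.

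Section 10.4.11 hopes the exploratory results will help to plan a larger study, so counts that are not comparable between participants, or with the 6-month shelter outcome, would be a poor input.

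**Working it through.** The plan states no figure for this outcome, so there is nothing to reproduce. The check sizes each consequence and asks what it depends on.

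**Inputs**
- 6 months = 365.25 / 2 = 182.6 days (convention; the plan does not convert months to days).
- Window: -14 and +56 days (Section 7.3.4, Attachment A).
- About 40 participants (Section 10.5).
- Visit rates and the shares seen early or late: not given, so assumed below.

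**Range of review dates**
- Earliest: 182.6 - 14 = 168.6 days.
- Latest: 182.6 + 56 = 238.6 days.
- Spread: 70 days.

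**Reading A: counts cut at 6 months**
- Reviewed at or after month 6: full observation, and equal for everyone.
- Reviewed at -2 weeks and not reopened: 14 / 182.6 = 7.7% short.
- Effect on the sample mean if a share e is reviewed at -2 weeks, with an even visit rate: e x 14 / 182.6. For e = 0.10, 0.25 and 0.50 (4, 10 and 20 of 40) this is 0.8%, 1.9% and 3.8%.

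**Reading B: counts run to the review date**
- Longest against shortest: 238.6 / 168.6 = 1.42.
- Latest against month 6: 238.6 / 182.6 = 1.31.
- Turning these ratios into a bias in the mean needs a share of late visits, which the plan does not give. Placing 10% to 50% of participants at the outer limit gives 0.10 x 56 / 182.6 = 3.1% to 0.50 x 56 / 182.6 = 15.3%. These figures hold only under Reading B, and only with every late participant at exactly +8 weeks.

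**Which reading the text supports**
- No section says that counts run to the review date.
- The only period attached to a record-based outcome is 6 months from the ED intervention (Sections 4.2.3 and 10.4.11).
- The Protocol Summary frames exploratory comparisons as baseline against 6 months.
- Section 8.1 describes a retrospective record, and hospital encounters are dated events. A late review therefore loses nothing, because later visits can be left out of the count.

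Reading A is the ordinary one.

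**Scale against chance variation**

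Under a Poisson model, the relative standard error of a mean count in 40 people is 1 / sqrt(40 x mean). Assumed rates of 0.5, 2 and 4 visits a year give 6-month means of 0.25, 1 and 2, and relative standard errors of 32%, 16% and 11%. Counts more variable than Poisson would make these larger. The Reading A shortfall of 0.8% to 3.8% is small beside them.

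**The case for a change.** The best case for a change is that the gap is wider than an end date. Every participant is a Bellevue ED patient on day 0 and is referred that day to hospital substance use services, and no visible rule says whether those contacts count. Someone who never attends the final visit has no date to anchor the review, although the dataset covers all participants. The abstraction tool may settle all this, but Section 17 places attachments outside the protocol and lets them change without amendment. Section 10.1 says there is no formal SAP, so Section 10 is the only fixed place for a rule. A sentence would cost almost nothing.

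Some of this stands. The protocol body is silent, and naming the period in Sections 4.2.3 and 10.4.11 would be tidier. But the consequences are slight:

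- The index ED visit occurs once for everyone, so counting it adds the same one visit to each total and does not disturb comparisons between participants. It would matter in a before-after comparison of EMR counts, but Section 10.4.11 attaches the comparison with baseline to the self-reported measures.
- Reading a chart needs no contact with the participant, so non-attendance does not prevent it. Section 5.7 covers whose records may be used.
- The early shortfall assumes that the visit window governs the chart review to the day and that the chart is never reopened. The text says neither.

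**Conclusion.** No change to the plan is called for. The wording leaves a definition unwritten in the visible text. The abstraction tool may already supply it, and if not, an analyst would ordinarily cut dated visits at 6 months, as for shelter entry.

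The most that can be tied to the stated window is a shortfall of 14 days, or 7.7%, for a participant whose chart is read at the earliest permitted date and not reopened. Even that presumes a 6-month EMR period, which the visible text does not state. The ratios of 1.42 and 1.31 require counting to the review date, which no section says.

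Little rests on the result. There is one arm, so no between-arm bias can arise. The outcome is exploratory and unpowered, and the hypothesis in Section 10.2 concerns housing and substance use only. The data sources listed in Section 4.2.1 for the primary feasibility endpoints do not include the EMR review. The conclusion assumes that visit dates are available from the record. It would need another look if the abstraction tool recorded only undated totals up to the review date.

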### Schematic of Study Design

CONFIDENTIAL

CONFIDENTIAL

### CONFIDENTIAL

## 2 Introduction, Background Information and Scientific Rationale

### 2.1 Background Information and Relevant Literature

Homelessness prevention: promise and challenges. Evidence is mounting that timely yet relatively brief interventions can prevent people from having to enter a homeless shelter. Homelessness prevention is of increasing interest to policy-makers and has been expanded in the U.S. over the last several years. So far prevention interventions have been implemented in populations including families, veterans, and people with mental illness leaving treatment. Specific interventions have included time-limited rental subsidies or back-rent payments, landlord mediation, improved institutional discharge planning, and other short-term crisis interventions. Such interventions have been successful in averting homelessness even in environments marked by structural issues like tight housing markets and low affordable housing availability. One challenge with prevention efforts, however, has been efficiently targeting services to people who are likely to become homeless in the absence of an intervention. In addition, prevention services are usually only provided to those people who seek them, missing people who are unaware of or unable to access such services.

Emergency departments as sites for homelessness risk screening and prevention. The emergency department (ED) may be an ideal location for homelessness risk screening and prevention, reaching people who are at high risk for homelessness and who might not otherwise access specialized prevention services. The Veterans Health Affairs system has implemented universal homelessness screening and referral in its clinics, yet no research has explored homelessness prevention among ED patients. More than 130 million visits are made to U.S. EDs each year. As the health care “safety net,” EDs care for the most vulnerable populations in our society. EDs are mandated to care for anyone who walks through their doors for any reason, making them uniquely accessible among health and social service sites. People turn to EDs not just during health crises, but also during life crises. A VA study found a statistically significant increase in the number of ED visits veterans make in the 30 days prior to becoming homeless. A study of new homeless shelter entrants in New York found that 34% had used an ED in the past year. A disproportionate share of ED patients are homeless or at risk for homelessness. For example, a survey of all patients presenting over 24 hours in three Michigan EDs found that 3.5% had been evicted in the past year and 16% lived in crowded housing. A survey of 1,500 Philadelphia ED patients found that 18.1% reported housing instability. Other surveys of ED patients have found high levels of food insecurity, low income, and other risk factors for homelessness. In a preliminary study of 625 randomly selected Bellevue Hospital ED patients surveyed over the course of 3 months, 30.5% had a history of homelessness in their lifetimes and 19.8% had been homeless in the past year. Among those not currently homeless, 18% were worried about having stable housing in the next 2 months. Further, 9.1% had been evicted at least once in the past year.

ED patients with unhealthy alcohol or drug use may be at even higher risk of homelessness than other ED patients given the strong associations between homelessness and substance use. One study of 19,055 ED patients found that those who screened positive for substance use had very high rates of homelessness or unstable housing: 22.8% were currently living in a shelter or on the streets and an additional 36.1% were “doubled up” with family or friends. With more than 5.1 million visits for substance use-related problems annually and nearly one-third of ED patients screening positive for unhealthy alcohol or drug use, EDs may be important sites for interventions to prevent homelessness among substance users. Given that only a small subset of substance users and people who are homeless access specialty substance treatment programs, and that both populations face barriers to accessing primary care, ED-based prevention programs have the potential to reach more people—and potentially more vulnerable people—than interventions at other sites.

Summary. EDs have potential as important health care delivery settings for homelessness prevention efforts among all patients, and particularly among patients with unhealthy alcohol or drug use. In earlier research, we developed an empirically-based homelessness risk screening tool (HRST) to identify ED patients at high risk for future shelter entry. We also conducted qualitative interviews with ED patients to learn about their pathways to homelessness and thoughts about future homelessness prevention

